### 6.2 Effectiveness Observation Items

**(1) Joint swelling and pain relief rate: After the first dose, DAS 44 score was < 1.6, and decreased by more than 0.6 before and after treatment.**

Disease Activity Score of 44 Joints Based on CRP (DAS 44 -CRP): It assesses the degree of joint swelling and pain. The calculation formula is as follows:

$$\text{DAS44 - CRP} = 0.54 \times \sqrt{RAI} + 0.065 \times \sqrt{SJC44} + 0.17 \times \ln(CRP + 1) + 0.072 \times GH + 0.45$$

**44 assessed joints:** including both hand metacarpophalangeal joints (MCP1-5), proximal interphalangeal joints (PIP2-5), thumb interphalangeal joints, both wrists, both elbows, both shoulders and both knees, as shown in the figure below:

**Swollen joint count (SJC):** The number of swollen joints among 44 joints was recorded .

**CRP level:** Record laboratory test results in mg/dL (CRP).

**VAS score:** Patients mark the disease activity on a 0-100 mm visual analog scale based on their own feelings, with 0 representing no activity and 100 representing extreme activity.

2) Disease activity grading of joint swelling and pain (based on DAS 44 score):

Low activity ( DAS 44 < 1.6 )

Moderate activity ( 1.6≤DAS44 < 2.4 )

High activity ( 2.4≤DAS 44 ≤ 3.7 )

Severe activity (DAS 44 > 3.7 )

3) Evaluation of treatment response at the time of disease remission (based on reduction in DAS 4 score):

Good response (DAS 44 >1.2)

General response (0.6<DAS 44 ≤1.2)

No response (DAS 44 ≤ 0.6)

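### As printed, the swollen-joint term of the DAS44-CRP is worth at most 0.43 points, so with the other components unchanged, clearing of swelling alone cannot pass the 0.6 response cut-off

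*Protocol*

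**What the plan says.** The relevant text is all in Protocol section 6.2, item (1). The endpoint is a relief rate for joint swelling and pain. It is listed first, in bold, both there and in the Program Summary.

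- **Purpose of the score.** Of the DAS44-CRP the section says: "It assesses the degree of joint swelling and pain".
- **Relief rule.** Relief requires "DAS 44 score was < 1.6, and decreased by more than 0.6 before and after treatment".
- **Formula.** DAS44-CRP = 0.54 × √RAI + 0.065 × √SJC44 + 0.17 × ln(CRP + 1) + 0.072 × GH + 0.45.
- **Swollen-joint count.** "The number of swollen joints among 44 joints was recorded". The joints named in the text number 28.
- **Activity bands.** Low activity is a score below 1.6. Higher bands begin at 1.6 and 2.4, and the top band lies above 3.7.
- **Response grades.** These are introduced as based on the reduction in the score. The lowest reads "No response (DAS 44 ≤ 0.6", the middle one "General response (0.6<DAS 44 ≤1.2", and a good response is a reduction above 1.2.

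No separate criterion for swelling is given. RAI and GH are not defined. A patient rating on a "0-100 mm visual analog scale" is described, but the text does not link it to GH.

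**The concern.** An endpoint named for swelling should be able to register swelling going away. Here the swelling component has both a small coefficient and a square root, while the smallest response the plan recognises is a fall of more than 0.6. If the whole range of the component is smaller than that step, the endpoint is in practice driven by RAI, the patient rating and CRP.

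A group difference confined to swelling could then be missed, and a difference in the other components would be reported under a label that mentions swelling. The formula determines every patient's score, activity band and response grade. If the printed term is a transcription slip, every result in a patient with swollen joints is affected.

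**Working it through.** The protocol states no maximum for the term, so there is no figure to reproduce. The printed formula is evaluated directly.

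**1. Range of the swelling term, 0.065 × √SJC44**

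| Swollen joints cleared | Fall in score, as printed |
|---|---|
| 1 | 0.065 |
| 10 | 0.065 × 3.162 = 0.206 |
| 20 | 0.065 × 4.472 = 0.291 |
| 28 | 0.065 × 5.292 = 0.344 |
| 44 | 0.065 × 6.633 = 0.431 |

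The count of 28 comes from the named joints: 10 MCP + 8 PIP + 2 thumb IP + 2 wrists + 2 elbows + 2 shoulders + 2 knees.

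**2. Against the cut-off.** With RAI, CRP and GH unchanged, a fall of 0.6 would need (0.6 / 0.065)² = 85.2 swollen joints, on a count that stops at 44. Because the terms add, this does not depend on the values of RAI, CRP or GH. At (RAI, CRP, GH) = (0, 0, 0), (1, 1, 5), (4, 1, 10) and (9, 3, 30), going from 44 swollen joints to none lowers the score by 0.431 each time.

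**3. Against the activity bands.** With 44 swollen joints and RAI, CRP and GH all at 0, the score is 0.45 + 0.431 = 0.881. Adding a CRP of 10 mg/dL contributes 0.17 × ln 11 = 0.408, giving 1.289. Both are in the low-activity band, so the level half of the relief rule is met with every joint swollen.

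**4. Swelling unchanged, good response.** SJC44 stays at 44 while RAI goes 4 to 0, CRP 1 to 0 and GH 10 to 5.
- Before: 1.080 + 0.431 + 0.118 + 0.720 + 0.45 = 2.799
- After: 0 + 0.431 + 0 + 0.360 + 0.45 = 1.241
- Fall: 1.558. This is above 1.2 and the score ends below 1.6, so the patient is a good responder and meets the relief rule.

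**5. Swelling deciding the result.** After full clearing of 44 joints, the other terms need to supply only a little more than 0.6 − 0.431 = 0.169. If GH is in mm (an assumption), that is 0.169 / 0.072, about 2.35 mm. With RAI 1 and CRP 1 throughout and GH 8 to 5:
- swelling 44 to 0: 2.115 to 1.468, a fall of 0.647, relief rule met
- swelling stays at 44: 2.115 to 1.899, a fall of 0.216, relief rule not met

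**6. Sensitivity to the root only.** Without the square root, clearing 10 joints would give 0.065 × 10 = 0.65 instead of 0.21, and 44 joints 2.86 instead of 0.43. The protocol does not say that this form was meant. The comparison shows only that the root decides whether swelling can move the grade by itself.

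**The case against.** The strongest reply is that the grade rests on the total score. A low weight on one component is a property of a composite, and the protocol nowhere promises that swelling alone will produce a response. That stands, and it limits the point. A reader might infer that clearing of swelling is always graded as no response, that the endpoint cannot register swelling at all, or that a treatment which clears swelling would be reported as ineffective. The documents support none of these without the condition that RAI, CRP and GH do not change; step 5 is a counter-example. A smaller one: RAI 1 to 0 alone gives 0.54, and one cleared swollen joint brings it to 0.605. Nothing in the protocol indicates how often swelling would clear while the other components stay still.

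Three further inferences also fail.

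- **One RAI point outweighs 44 swollen joints.** This is true only for the step from 1 to 0 (0.54). From 4 to 3 it is 0.54 × (2 − 1.732) = 0.145, well under 0.431.
- **Activity grades come out too low.** This presumes a different correct formula. It also depends on GH: if GH is the 0–100 mm rating, a patient is in the top band once GH exceeds (3.7 − 0.45) / 0.072, about 45.1 mm, with no swollen joint.
- **The root is an error.** The documents do not settle this. A root sign is a single symbol that can be gained or lost when an equation is converted, so the typeset page should be checked as well.

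The reply does not remove the mismatch inside the section. A component that cannot reach the smallest response step even over its full range sits badly in an endpoint named for it. Nor is this detail left to a later analysis plan, since the protocol itself prints the formula and the cut-offs.

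**Conclusion.** The point holds in conditional form. As printed, swelling can contribute at most 0.43 (0.34 on the 28 named joints) towards a required fall of more than 0.6. With the other components unchanged, clearing of swelling in every joint is graded as no response, and persistent swelling in all 44 joints is compatible with a good response. The endpoint therefore cannot show relief of swelling on its own and gives it very little weight.

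The cap rests only on the printed coefficient, the root and a count of at most 44; it does not depend on the GH scale or the CRP unit. The worked examples in steps 4 and 5 use illustrative values of RAI, CRP and GH. Whether the printed term is what the sponsor intended remains open.

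**What to change.** Before any score is computed, check the swollen-joint term, including its square root, against the sponsor's source for the score, and correct it if it was mis-transcribed. Use that one verified formula for the relief rule, the activity bands and the response grades. In the same check, state what RAI and GH are and reconcile the 28 named joints with the count of 44, since both bear on the same calculation.

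Whichever form stands, report change from baseline in SJC44 by group as a separate result, so that an effect on swelling is visible. The count is already recorded under section 6.2, so no new swelling data are needed. The cost is a line of derivation code, a short protocol correction if the term changes, and one extra table.

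### Section 6.2 defines a 44-joint score, but the joints it names total 28, with none below the knee

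*Protocol*

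**What the plan says.** Protocol section 6.2, item (1), names the instrument the "Disease Activity Score of 44 Joints Based on CRP". Under the heading "44 assessed joints" it gives the joints as "including both hand metacarpophalangeal joints (MCP1-5), proximal interphalangeal joints (PIP2-5), thumb interphalangeal joints, both wrists, both elbows, both shoulders and both knees", and then refers the reader on with "as shown in the figure below". The swollen count is defined on the same total: "The number of swollen joints among 44 joints was recorded".

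The score is 0.54 × √RAI + 0.065 × √SJC44 + 0.17 × ln(CRP + 1) + 0.072 × GH + 0.45. The text does not say which joints RAI covers.

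The score drives the relief rule ("DAS 44 score was < 1.6, and decreased by more than 0.6 before and after treatment"), the four activity grades and the three response grades. Joint pain and swelling relief is also the first effectiveness item in the Program Summary. No other section of the protocol lists the joints.

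**The concern.** The label and the swollen count say 44, while the list gives exact finger ranges and large joints that do not add up to 44. The knees are the only lower-limb joints named; no ankle, foot or toe joint appears. Two careful assessors could read the same section and examine different joints.

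At stake is the measurement behind the first-listed outcome. If swelling or tenderness sits in joints that are not examined, the score is too low at that visit, and a change in those joints does not enter the before-and-after difference. A joint that was not examined cannot be scored later, so analysis cannot repair this.

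**Working it through.** **Inputs.** The joint list, the stated total of 44, the score weights and the relief rule all come from section 6.2. The RAI values below are assumptions for illustration.

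**Step 1: count the named joints, both sides.**

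| Joint group | Count |
|---|---|
| MCP 1–5 | 5 × 2 = 10 |
| PIP 2–5 | 4 × 2 = 8 |
| Thumb IP | 2 |
| Wrists | 2 |
| Elbows | 2 |
| Shoulders | 2 |
| Knees | 2 |
| **Total** | **28** |

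The stated 44 is not reproduced: 44 − 28 = 16 joints, or 16/44 = 36%, are unnamed. Counting a first PIP joint on each hand in addition to the thumb IP gives 30, which still falls short.

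**Step 2: direct effect through the swollen count.** This is the only term that the text explicitly ties to the 44 joints.

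- All joints swollen: 0.065 × (√44 − √28) = 0.431 − 0.344 = 0.087.
- Largest possible loss, when only the 16 unnamed joints are swollen: 0.065 × √16 = 0.26.

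The loss at any visit therefore lies between 0 and 0.26. The error in a before-and-after difference is one such loss minus another, so it lies between −0.26 and +0.26. This is enough to move a patient who is near 1.6 or near a fall of 0.6, but it cannot by itself make up a fall of 0.6.

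**Step 3: possible effect through RAI.** This assumes that RAI is a sum over joints scored on the same short list.

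| RAI in listed joints | RAI in unlisted joints | Loss = 0.54 × (√total − √listed) |
|---|---|---|
| 0 | 1 | 0.54 |
| 0 | 4 | 1.08 |
| 9 | 1 | 0.088 |
| 9 | 4 | 0.327 |

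The loss is large when the listed joints are quiet and modest when they are already tender.

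**Step 4: direction.** Under the same assumption, with the other terms held constant, the error in the fall can go either way.

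- RAI 4 at baseline, all in unlisted joints, and 0 afterwards. The full score falls by 0.54 × √4 = 1.08 and meets the fall criterion. The short-list score does not fall.
- RAI 9 at baseline (5 listed, 4 unlisted), and 4 afterwards, all unlisted. The full score falls by 0.54 × (3 − 2) = 0.54 and misses the criterion. The short-list score falls by 0.54 × √5 = 1.21 and meets it.

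**The case against.** The strongest defence is that the list opens with a word that need not mean a complete list and ends by pointing to a figure that cannot be seen here. If the figure shows all 44 joints, the defect is an incomplete sentence beside a correct figure and a correct total. That stands as a limit on the conclusion: the documents do not show which set the sites will use. It does not make the text consistent. A list with exact finger ranges under a heading of 44 reads as a definition, and it gives 28.

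A second defence also stands: the swollen-joint term has a small weight. Every effect above 0.26 runs through RAI and rests on a joint set that the protocol does not state.

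Three stronger readings are tempting, but the documents do not support them.

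- **A patient with disease only in unlisted joints cannot show relief.** The CRP and GH terms can also fall. With RAI and swollen count at zero, CRP left out, and GH taken as the 0–100 mm scale, a fall in GH from 50 to 5 moves the score from 0.45 + 3.60 = 4.05 to 0.45 + 0.36 = 0.81. With GH on a 0–10 scale, a fall from 10 to 1 lowers the score by 0.648, to 0.522. Both meet the relief rule. (The GH values are illustrative.) What goes unmeasured is the improvement in those joints.
- **The inconsistency biases the comparison of cohorts through hospitals.** Section 4.4 groups patients by actual prescription at each centre and says nothing about prescribing clustering by hospital. Sections 9.1.2 and 9.4 plan a unified SOP and training. These do not correct the list, but a hospital-linked bias remains a possibility, not a finding.
- **The DAS44 cut-offs are wrong and those of a 28-joint instrument should replace them.** The documents contain no 28-joint formula or cut-offs, so this cannot be checked from them. Nor do they say which joints make up the missing 16.

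**Conclusion.** The point holds as an internal contradiction. Section 6.2 states 44 joints and names 28, and this needs no assumption beyond counting both sides. The joint definition of the first-listed outcome is wrong as written.

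The demonstrated size is modest. Through the swollen count, an assessor who follows the list loses 0.087 points at maximum counts and never more than 0.26, which matters only for patients close to a threshold. A loss above 0.6, such as 1.08 for an RAI of 4 lying wholly in unlisted joints, is conditional on RAI being scored on the same short list. Which joint set the sites will examine, and how often a classification would change, cannot be determined from the protocol.

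**What to change.** Make the written list, the figure, the swollen count and the CRF name one and the same joint set. State in section 6.2 which joints RAI uses, and apply the set at every centre.

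- **If 44 joints are intended:** write out all 44 in section 6.2.
- **If only the 28 listed joints are examined:** rename the score and the SJC44 term throughout, and justify the formula, the 1.6 and 0.6 thresholds and the activity and response grades for that joint set.

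The cost is protocol and CRF wording, plus up to 16 more joints per examination if 44 is kept. No additional visit is needed.

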	D5 or before discharge: complete blood count, CRP, and chikungunya nucleic acid tests; Follow-up after treatment; telephone follow-up on D7, D14, and D28.
General information and medical history	1. Demographic information: gender, age, height, weight, ethnicity, etc.; 2. Medical history: past medical history, current medical history, epidemiological history and allergy history.
Effectiveness evaluation	

1. Joint Pain and Swelling Relief Rate (DAS44 Score)

2. Change in Rash Severity (Modified EASI Score)

3. Time to Complete Fever Resolution

4. Time to Viral RNA Clearance (RT-PCR Negative)

5. Recovery of Laboratory Markers

6. Time to Symptom Recovery

7. Incidence of Complications

Safety evaluation	Incidence of adverse events/adverse reactions.

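### The DAS44-CRP formula leaves GH and RAI undefined; read with the only activity scale given (0-100 mm), the patient's self-rating can block relief or produce a response grade while joints and CRP stay the same

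*Protocol*

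**What the plan says.** Section 6.2, item (1), prints the score as

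DAS44-CRP = 0.54 × √RAI + 0.065 × √SJC44 + 0.17 × ln(CRP + 1) + 0.072 × GH + 0.45.

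Of its purpose the protocol says: "It assesses the degree of joint swelling and pain".

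The text after the formula explains three quantities:
- the swollen joint count: "The number of swollen joints among 44 joints was recorded";
- CRP, to be recorded in mg/dL;
- a VAS score: "Patients mark the disease activity on a 0-100 mm visual analog scale based on their own feelings".

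RAI and GH appear only inside the formula. The VAS is described but does not appear in the formula under that name.

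Three classifications depend on the score:
- Relief: "DAS 44 score was < 1.6, and decreased by more than 0.6 before and after treatment".
- Activity grade, with cut-offs at 1.6, 2.4 and 3.7, the top band being "Severe activity (DAS 44 > 3.7".
- Response grade by size of the reduction, with cut-offs at 0.6 and 1.2, the best being "Good response (DAS 44 >1.2".

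The Program Summary lists "Joint Pain and Swelling Relief Rate (DAS44 Score" as the first effectiveness item.

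**The concern.** Two of the four inputs to the score have no definition, unit or range. For one of them, GH, the natural candidate is the 0-100 mm VAS. That reading fits badly with the printed weight and cut-offs: a term running to 7.2 points stands beside activity cut-offs that end at 3.7. A score presented as a measure of joint swelling and pain could then be driven mainly by a single self-rating.

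At stake is who counts as relieved, who counts as a responder, and which activity grade each patient receives. If centres enter GH in different units, or a later analyst rescales it, the relief rate changes for reasons unrelated to treatment. Section 4.4 forms the groups from what was actually prescribed, so patients can be expected to know their treatment. A score dominated by self-rating would be correspondingly more open to expectation effects.

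RAI raises a separate problem. Section 6.2 gives no instruction to record it, and the flow chart has no row that names it. If it is not captured, the score cannot be reconstructed.

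**Working it through.** The protocol gives no worked DAS44 value to reproduce, so the check evaluates the printed formula directly.

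**Inputs (all from section 6.2):** weights 0.54, 0.065, 0.17 and 0.072; constant 0.45; SJC from 0 to 44; CRP in mg/dL; VAS from 0 to 100 mm; cut-offs 1.6 / 2.4 / 3.7 for activity and 0.6 / 1.2 for the reduction. **Assumption A:** GH is the VAS in mm. **Assumption B (for contrast, not in the protocol):** the same VAS is entered as 0-10.

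**1. Size of the terms**
- GH under A: 0.072 × 100 = 7.2. Under B: 0.072 × 10 = 0.72.
- Swollen joints, maximum: 0.065 × √44 = 0.431, which equals 0.431 / 0.072 = 6.0 mm of VAS.
- CRP at assumed values of 1, 10 and 30 mg/dL: 0.12, 0.41 and 0.58.
- RAI: the range is not stated. To match 7.2 it would have to reach (7.2 / 0.54)² = 177.8.

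**2. VAS that reaches each activity cut-off under A, with RAI = SJC = CRP = 0:** (cut-off − 0.45) / 0.072

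| Cut-off | VAS needed | Consequence |
|---|---|---|
| 1.6 | 15.97 mm | relief blocked; grade moderate |
| 2.4 | 27.08 mm | grade high |
| 3.7 | 45.14 mm | grade severe above this |

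The maximum is 0.45 + 7.2 = 7.65, and 100 − 45.14 = 54.9% of the VAS length falls in the severe band. Under B the same patient scores at most 0.45 + 0.72 = 1.17, always low.

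**3. VAS fall that crosses each response cut-off under A, all else unchanged:** reduction / 0.072
- 0.6 / 0.072 = 8.33 mm. A larger fall moves the patient out of the no-response grade.
- 1.2 / 0.072 = 16.67 mm. A larger fall gives a good response.

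Example: VAS from 60 to 40 mm gives 0.072 × 20 = 1.44, a good response. Under B it gives 0.072 × 2 = 0.14, no response. Under B even a full-scale fall gives only 0.72, so VAS change alone can never give a good response.

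**4. Effect on relief (constructed values).** Baseline RAI 9, SJC 9, CRP 3, VAS 60 mm; afterwards RAI, SJC and CRP all 0, VAS 20 mm.
- Under A: 1.62 + 0.195 + 0.236 + 4.32 + 0.45 = 6.82, falling to 0.45 + 1.44 = 1.89. Not relieved, because 1.89 is not below 1.6.
- Under B: 1.62 + 0.195 + 0.236 + 0.432 + 0.45 = 2.93, falling to 0.45 + 0.144 = 0.59. Relieved.

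**5. Limit on what GH can do.** With SJC, CRP and GH all 0:
- RAI reaches the 1.6 cut-off at ((1.6 − 0.45) / 0.54)² = 4.5.
- RAI gives severe above ((3.7 − 0.45) / 0.54)² = 36.2.

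A low VAS therefore does not secure relief or a low grade when RAI is raised.

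**The case against.** **The size is conditional.** It depends on GH being the VAS in mm and on a weight read by machine from a PDF. One lost zero in the weight (an assumption) would cut the maximum from 7.2 to 0.72 and remove nearly all of the effect. This stands: the figures describe a reading of the document, not an established property of the score. It does not touch the missing definitions of GH and RAI, which do not depend on the weight.

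**If position identifies GH as the VAS, the unit is given.** It is then mm, and the complaint of an undefined unit weakens. That is fair. What remains in that case is a weight that does not sit sensibly with the stated scale and cut-offs. Either way the text needs correcting. The 0-10 alternative appears nowhere for disease activity; the only 0-10 VAS in section 6.2 is for itching.

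**The zero-component thresholds are artificial.** Severe pain in multiple joints is part of the clinical picture in section 4.1.1, so RAI, SJC and CRP will rarely all be 0 at baseline. This also stands, and the thresholds in steps 2 and 4 show relative weight rather than a typical patient. The response thresholds in step 3 hold at any fixed level of the other terms.

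**Other documents may settle it.** Section 8.2 plans variable descriptions, section 9.1.2 a unified SOP, and a statistical analysis plan may exist. These could supply definitions. They would not correct what section 6.2 prints, and they could not recover RAI if it was never recorded.

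A reader might go further and infer that GH alone decides relief and every grade. The documents do not support that: step 5 shows that RAI by itself can keep the score at or above 1.6, or make it severe, with GH at 0. A reader might also infer that the weight is proven wrong. Nothing in the protocol shows whether the weight or the scale is at fault.

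**Conclusion.** The point holds as a fault in the definition of an endpoint. No figure stated in the protocol is miscalculated.

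**Firm, without assumptions:** GH and RAI are undefined, the activity VAS is not linked to GH by name, and no rescaling is stated.

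**Conditional on GH being the VAS in mm and on the printed weight being read correctly:** the self-rating contributes up to 7.2 points against at most 0.43 for swollen joints. It can block relief and raise the activity grade, and a fall of more than 16.7 mm yields a good response with joints and CRP unchanged. It cannot override a raised RAI to secure relief or a low grade.

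The protocol names no primary endpoint, but this score defines the first-listed effectiveness item and two sets of grades. Two plausible ways of entering GH classify the same patient differently. It should be settled before data are scored, with high confidence in the missing definitions and less in the exact size of the effect.

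**What to change.** In section 6.2 and the CRF:
1. Check the printed formula, and the GH weight in particular, against its source.
2. Define GH and RAI with units and ranges, and state whether GH is the VAS.
3. Reconcile the GH weight with the VAS unit so that the score fits the 1.6 / 2.4 / 3.7 and 0.6 / 1.2 cut-offs.
4. Record raw RAI, SJC, CRP and VAS, and compute the score centrally from them rather than at the sites.

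The cost is a short correction to section 6.2 and the CRF, plus central programming of one formula. SJC, CRP and the VAS are already described as recorded. RAI is one added CRF item if it is not already captured. If the raw values are kept, scores already entered can be recomputed; without RAI they cannot.
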